Accelerometer Analysis. Raw data from the accelerometer will be pre-processed using ActiLife v6.4 software, and integrated into 60-second and 10-second epochs for assessing wear/non-wear intervals and time spent in various physical activity intensities, respectively. Non-wear will be defined as at least 60-minute intervals of “zero” activity counts with 2-min incidental wear intervals allowed. Wear intervals lasting less than 30 minutes will be classified as non-wearing. Total daily wear time will be calculated by subtracting non-wear time from 24 hours. Primary analyses will use total volume of physical activity, expressed as the mean counts per minute over the duration of accelerometer monitoring. Secondary analyses will use percentage of time spent in commonly used domains of physical activity intensity (sedentary, light, moderate, and vigorous).

6.3.3. Specific Aim 3. Separate regression models will be used to explore associations between changes in fear of movement and pain self-efficacy and changes in pain, disability, general health, and physical activity from baseline to 6 and 12 months after surgery for the entire sample. We will construct a mediation model that estimates the effect of the mediation by changes in fear of movement and in pain self-efficacy on outcomes as the result of surgery. This comprises 3 sub-models that relate (1) the treatment to health outcomes directly, (2) the treatment to fear of movement and pain self-efficacy and (3) both the treatment and fear of movement and pain self-efficacy to health outcomes simultaneously. This will demonstrate any mediation effect, if present, by seeing how the relationship between treatment and outcomes changes when the potential mediators are added or removed.

6.3.4. Specific Aim 4. Regression models will be used to explore the interaction between patient characteristics and treatment for each outcome in the entire sample. Important sub-groups will be identified based on the strength of association between the response to treatment (change in outcomes) and each covariate included in the model (i.e., patient age, type of surgery, depressive symptoms). To illustrate, consider the simplified model with just one covariate:

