$y_i^{(1)} - y_i^{(0)} = \mu + \beta_1 I(\text{treat}_i) + \beta_2 x_i + \beta_3 x_i I(\text{treat}_i) + \epsilon_i$ where x_i is some covariate of interest from the list above. β_1 , β_2 and β_3 are parameters for the treatment, covariate and treatment-by-covariate interaction, respectively. Sub-groups that show a stronger response to treatment will have relatively large, negative interaction parameter values, indicating that they would reduce the outcome score beyond treatment in the absence of the covariate.

6.4. Missing data. Missing data are a serious concern that complicates the interpretation of the study results. We will address this issue from both a trial conduct and analysis perspective. Regarding trial conduct, we will

1. Limit participant burden and inconvenience in data collection
2. Provide compensation for participation and completion in the study
3. Select high quality investigators
4. Provide pre-study training of investigators as well as on-study reinforcement
5. Monitor and report missing data rates during the trial
6. Emphasize the importance of full participation in the trial during the consent process
7. Collect information on the reasons for missing data
8. Actively engage participants in the study and educate them about the importance of their engagement

9. Collect surrogate information on participants who miss clinic visits
10. Hold regular CBPT meetings to discuss strategies for enrollment and engagement of participation
11. Set targets for acceptable rates of missing data

While these efforts will help to minimize missing data, we recognize that missing data are inevitable.

Our use of Bayesian estimation procedures will allow us to easily impute missing data within our models. In most cases, this will allow us to use data with some missing values, and avoid the information loss that is inherent in complete case analysis. Where it is unlikely that values are missing at random, we will include an imputation sub-model that uses available covariates to account for plausible patterns of non-random missingness. Though it is not possible to demonstrate that data are missing at random, including as many predictor variables in the imputation model as possible generally increases the chances that the missing at random assumption (conditional on the covariate values) is reasonable.

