6.5. Justification of Sample Size in the Randomized Trial. We estimated power for the study, based on a target of 110 patients per arm with complete follow-up data at 12 months. Power was estimated by generating simulated data, then using the simulated data to try to estimate the original model parameters. We are interested in determining whether the model can estimate the effects of the treatment with adequate precision. We used a simplified model of treatment effect, a fixed effect model that describes the difference between measurements at the baseline $y^{(0)}$ and after treatment $y^{(1)}$:

$$y_i^{(1)} - y_i^{(0)} = \mu + \beta I(\text{treat}_i) + \epsilon_i$$

where $\epsilon_i \sim N(0, \sigma^2)$ is the residual for individual i , and I is the indicator function, here evaluating to 1 if the individual is in the treatment group and 0 otherwise. Thus, β describes the effect of the treatment, and μ the expected change in the absence of treatment. For Aim 4, power was measured with respect to the ability to distinguish a non-zero effect of the subgroup-treatment interaction effect (β_3).

We generated 200 simulated datasets by resampling available pilot data from a currently funded R21 project (1R21AR062880-01). Control subjects were resampled from control individuals in the pilot data, and treatment subjects were also resampled from control individuals, but with the target effect size added to the sampled values. Power was estimated by fitting Bayesian models to each of the simulated datasets for each response variable and recording the proportion of calculated 95% credible intervals (BCI) for β that excluded zero.

6.6. Interim analysis. A medical monitor is responsible for monitoring the accumulated interim data as the trial progresses to ensure patient safety and to review efficacy. During the first year of the study, involvement of the monitor will occur prior to randomizing the first patient. A conference call will be conducted to review study procedures and the monitoring of adverse events to ensure that a comprehensive safety monitoring plan is in place

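### The Aim 4 text reads a negative interaction as the stronger response for every outcome; that sign is reversed for SF-12, activity counts and walking speed

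*Combined protocol and SAP*

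**What the plan says.** Section 6.3.4 sets the scope: "Regression models will be used to explore the interaction between patient characteristics and treatment for each outcome in the entire sample". It then says how sub-groups are picked out: "Important sub-groups will be identified based on the strength of association between the response to treatment (change in outcomes) and each covariate".

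A worked form follows, introduced by "To illustrate, consider the simplified model with just one covariate". The response is the raw change from baseline, y(1) − y(0). The terms are treatment (β1), the covariate x (β2) and their product (β3). The text then gives the sign rule, "Sub-groups that show a stronger response to treatment will have relatively large, negative interaction parameter values", and its reason: "indicating that they would reduce the outcome score beyond treatment in the absence of the covariate".

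The only other statement about β3 is in section 6.5, where "power was measured with respect to the ability to distinguish a non-zero effect of the subgroup-treatment interaction effect". That criterion has no direction.

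Hypothesis 4 in section 6.1 does have one. It predicts greater improvement for CBPT participants who are 60 or older, have a fusion, or report clinically significant depressive symptoms before surgery.

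**The concern.** The models cover all outcomes, but the sign rule fits only scores where a fall is a benefit. The outcome list in section 6.2 mixes the two kinds, and SF-12 is one of its three primary measures. Nothing in the documents limits the rule to lower-is-better scores or reverse-scores the others.

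Applied literally to SF-12, activity counts or walking speed, the rule would name the sub-group that gains less from CBPT as the stronger responder. That is the opposite of what Hypothesis 4 asks. No other sentence in the plan ties the sign of β3 to benefit, so nothing else in the Aim 4 text corrects it.

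**Working it through.** The plan gives no figure for β3, so there is none to reproduce. The check is of signs.

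**Direction of benefit, from the documents**

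| Outcome | Where defined | Benefit is |
|---|---|---|
| ODI | 5.8.1: item scores rise with worse functioning | a decrease |
| BPI | 5.8.1: higher scores mean worse pain | a decrease |
| TUG | 5.8.2: important change is a shorter time | a decrease |
| SF-12 PCS and MCS | 5.8.1: 100 is best health | an increase |
| Activity | 5.8.2 and 6.3.2: mean counts per minute; Aim 2 seeks to improve activity | an increase |
| 10-Meter Walk | 5.8.2: recorded in m/sec; Aim 2 seeks to improve function | an increase |
| Chair Stand | 5.8.2: recorded unit not stated | not determined |

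**What β3 measures.** In the section 6.3.4 model the CBPT effect on change is β1 at x = 0 and β1 + β3 at x = 1. So β3 = (effect at x = 1) − (effect at x = 0).

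**Signs.** Assume a benefit of 1 unit at x = 0 and 2 units at x = 1, so that x = 1 is the stronger responder.

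- ODI, BPI, TUG time: β3 = −2 − (−1) = −1. The rule reads this as stronger, which is right.
- SF-12, counts per minute, m/sec: β3 = 2 − 1 = +1. The rule reads this as not stronger, which is wrong.

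In outcome units, again with assumed effects:

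- ODI effects of −5 and −10 give β3 = −10 − (−5) = −5, read correctly.
- PCS effects of +3 and +6 give β3 = 6 − 3 = +3. The sub-group that gains twice as much is read as the weaker responder.

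**Coding of x.** If x is replaced by 1 − x, the two effects change places. With the 1- and 2-unit benefits, ODI gives −1 − (−2) = +1 and SF-12 gives 1 − 2 = −1. Every sign flips, so the rule has no fixed meaning for any outcome until the coding is stated. Section 6.3.4 does not state it.

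**Separate point: baseline adjustment.** Section 6.3.2 adjusts the Aim 2 models for the baseline value of the outcome, and Appendix 9.4 shows that it is collected. The Aim 4 text names "each covariate included in the model (i.e., patient age, type of surgery, depressive symptoms") and does not mention it. Section 6.5 gives the numbers, "based on a target of 110 patients per arm with complete follow-up data at 12 months". The remaining inputs are assumptions, because the documents give no correlations: half of each arm has x = 1 (four cells of 55), the SD is 1 at both visits, and the baseline to follow-up correlation is r.

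- Residual variance without adjustment: 2(1 − r). With adjustment: 1 − r².
- SE(β3) = √(4 × variance / 55).
- Ratio of SEs = √[(1 − r²) / (2(1 − r))] = √[(1 + r)/2].

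| r | SE unadjusted | SE adjusted | Ratio | Reduction |
|---|---|---|---|---|
| 0.3 | √(4 × 1.40/55) = 0.319 | √(4 × 0.91/55) = 0.257 | 0.81 | 19% |
| 0.5 | √(4 × 1.00/55) = 0.270 | √(4 × 0.75/55) = 0.234 | 0.87 | 13% |
| 0.7 | √(4 × 0.60/55) = 0.209 | √(4 × 0.51/55) = 0.193 | 0.92 | 8% |

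**The case against.** The best defence is that the sentence belongs to an illustration and is not a decision rule. The plan selects sub-groups by strength of association and judges power by a non-zero interaction. Neither has a sign, and no estimate, interval or threshold depends on the sentence. Its own reason, that the score is reduced, suggests that ODI or BPI was in mind. An analyst would have to treat a fall in SF-12 as a gain to be misled, against section 5.8.1 and the wording of Aim 2.

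Most of this stands, and it is why the point is minor. It does not remove the error. The simplification that the illustration announces is a single covariate, not a single direction of scoring, and the sign sentence is worded generally under a heading that covers each outcome.

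A reader might go further and infer that the Aim 4 analysis will select the wrong sub-groups, or that its power is affected. The documents do not support that, because the stated criteria ignore the sign.

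A reader might also infer that leaving baseline out of the Aim 4 covariates is a mistake. That is not shown either. The list matches the characteristics in Hypothesis 4 and may name only the candidate effect modifiers. It also omits site, which Aim 2 includes, and the displayed model is labelled as simplified.

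**Conclusion.** The sign rule is wrong as written for SF-12 PCS and MCS, activity counts per minute and 10-Meter Walk speed. It is right for ODI, BPI and TUG time. Both statements assume that x = 1 marks the Hypothesis 4 sub-group, a coding that the plan leaves open. For Chair Stand the documents do not settle the direction. The percentage-time activity domains need a direction each, since less sedentary time and more moderate activity would move opposite ways.

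The error has no numerical size: it changes how a fitted coefficient is read, not the coefficient. The severity is minor.

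Baseline adjustment is a possible gain in precision, not a correction. Its 19% to 8% range depends on the assumed correlations, the equal SDs and, for the SEs themselves, the even split on x.

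**What to change.** Replace the sign sentence in section 6.3.4 with:

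> With x coded so that higher values (or x = 1) denote the sub-group named in Hypothesis 4, a stronger response is an interaction in the direction of improvement for that outcome: negative where lower is better (ODI, BPI, TUG time), positive where higher is better (SF-12 PCS/MCS, activity counts per minute, walk speed). The direction for Chair Stand and for each percentage-time activity domain will be stated according to how it is recorded.

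As an optional addition, state that the full Aim 4 change-score models also adjust for the baseline value of the outcome, as Aim 2 does.

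The cost is one replaced sentence and, if the addition is taken up, one covariate that is already collected. Data collection, the sample size and Aim 2 stay as they are.

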9.2. Summary of the CBPT Intervention by Session

Topics All Sessions include: Graded Exposure in Vivo; Goal-Setting; Problem-Solving
	
Major Content and Activities Each session builds upon the content of the previous session. Format includes: 1) review of previous session personally-tailored activity and walking goals and skills homework, 2) problem-solving barriers to completing goals, 3) introduction of new content through discussion and worksheets, and 4) review of homework assignment to be completed before next session.

Session 1: Goal Setting Introduction; Establish a Graded Activity Plan and Fear Hierarchy; Deep Breathing
	
Review purpose of the program, conduct semi-structured patient interview, explore gate control theory of pain, complete a graded activity plan and fear hierarchy, set activity goals based on hierarchy, explore walking history and set walking goals, introduce deep breathing as pain management strategy.

Session 2: Your Mind and Recovery Distraction Techniques; Progressive Muscle Relaxation
	
Check graded activity practice and activity goals, set new activity goals, review walking goals and set new goals, problem-solve barriers to completing goals, introduce distraction as pain management strategy and complete worksheet, introduce progressive muscle relaxation CD.

Session 3: Balance your Thinking Identify Negative Thoughts; Positive Self-Statements
	
Review activity and walking progress and set new goals, problem-solve barriers to completing goals, introduce event-thoughts-feeling-action handout, identify negative thoughts that effect activity using worksheet, practice replacing negative thoughts with positive self-talk and complete worksheet.

Session 4: Rest and Activity Activity Types; Pacing; Benefits of Program
	
Review activity and walking progress and set new goals, problem-solve barriers to completing goals, review activity types handouts, explore pacing strategies for pain management and complete worksheet, identify benefits of program so far and complete worksheet.

Session 5: Managing Setbacks Relapse Prevention Plan
	
Review activity and walking progress and set new goals, problem-solve barriers to completing goals, review relapse cycle handout, complete managing setbacks worksheet.


Session 6: Staying Healthy Pain Management Plan; Wrap-up
	
Review activity and walking progress, problem-solve barriers to completing goals, complete pain management plan worksheet, identify benefits of program so far and complete worksheet, reinforce importance of regular exercise and follow-up visits with surgeon and other health care providers.

9.3. Summary of the Education Intervention by Session

Topics	Major Content and Activities
Session 1: Physical Therapy	Review purpose of the program, conduct semi-structured patient interview, describe physical therapy, introduce benefits of physical therapy, describe different physical therapy techniques, and introduce different exercise programs.
Session 2: Promote Back Healing I	Discuss importance of proper posture and transitions, describe proper sleeping positions, and introduce ways to promote healing.
Session 3: Promote Back Healing II	Discuss importance of proper body mechanics, describe proper lifting techniques, and describe proper ergonomics at home and at work.
Session 4: Home Exercise	Describe the importance of a home exercise program (HEP), discuss the goals of a HEP, introduce the components of a HEP, and discuss the benefits of a HEP.
Session 5: Prevent Future Injury	Discuss ways to prevent re-injury, describe mechanisms of low back strain, introduce ways to manage a low back strain.
Session 6: Staying Healthy	Describe ways to stay healthy, discuss specific benefits of exercise and not smoking, and discuss ways to reduce stress, improve sleep, eat healthier, and conserve energy.

9.4. Data Collection Schedule

Assessment/Procedure	Pre-op	Baseline	6 month	12 month
Patient Consent	X			
Patient Characteristics				
Age, Gender, Race/Ethnicity	X			
Marital Status	X			
Educational Level	X			
Insurance Status	X			
Height/Weight	X			
Smoking Status	X	X	X	X
Working status	X	X	X	X
Medical History/Co-morbidities				
Pain Duration	X			
Prior Spinal Surgery	X			
Co-morbidities	X	X	X	X
Current medications	X	X	X	X
Intervening Events		X	X	X
Surgical Characteristics				
Type (fusion/no fusion)	X			
Spinal levels	X			
Revision (yes/no)	X			
Psychosocial Characteristics				
Fear of Movement (TSK)	X	X	X	X
Pain Self-Efficacy (PSEQ)	X	X	X	X
Depressive Symptoms (PHQ-9)	X	X	X	X
Expectations of Recovery	X			
Satisfaction		X	X	X
Primary and Secondary Outcomes				
Pain (BPI)	X	X	X	X
Disability (ODI)	X	X	X	X
General Health (SF-12)	X	X	X	X
Chair Stand	X	X		X
10 Meter Walk	X	X		X
Functional Mobility (TUG)	X	X		X
Physical Activity Counts (Accelerometer)		X	X	X
Health Services Utilization				
Physical Therapy Services	X	X	X	X
Narcotic Use	X	X	X	X
Re-hospitalization		X	X	X
Additional Surgery		X	X	X
